### **2.3. Randomization and Masking**

Children meeting inclusion criteria will be enrolled by local trained study personnel. At enrollment, children will be assigned a study identification number using the next unassigned number on a list identification numbers assigned to the site. Enrolled children will then undergo a baseline assessment. The baseline assessment includes data collection on demographics and socioeconomic status, anthropometric assessments, and a malaria rapid diagnostic test (RDT; see Figure 1 and Section 3 for details). After completion of the baseline assessment,

children will be randomized to receive either a single dose of directly observed oral azithromycin or a 7-day course of oral amoxicillin.

The randomization sequence will be generated by the UCSF investigators using R (R Foundation for Statistical Programming, Vienna, Austria). Children will be randomized in a 1:1 fashion to a single dose of azithromycin or a short course of oral amoxicillin. The randomization sequence will be linked to the study identification numbers. Randomized study arm assignments will be placed in sealed, opaque envelopes labeled with study identification numbers. When a child has been enrolled and has completed the baseline assessments, a CSPS nurse trained for the study will open the envelope to determine the allocation, and will administer study medication indicated as described in Sections 2.4 and 4.

To keep the allocation concealed, only the study nurse administering treatment will have access to the envelopes with the randomization allocations. The study nurse will open the envelope and administer treatment in a private room without the outcome assessor present. For each enrolled child, the study nurse will record whether or not azithromycin was administered on a paper form kept in a locked cabinet not accessible by the outcome assessor.

Given the nature of the intervention, participants and study personnel administering treatment will not be masked to treatment assignment. Outcome assessors will be masked to treatment assignment; this will be accomplished by assigning one CSPS nurse to administer treatment and a separate masked study team member to perform outcome assessments, including anthropometry, malaria RDT, and vital status updates.

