### Secondary Outcomes

- **Nutritional recovery by 8 weeks (Specific Aim 2).** Nutritional recovery will be defined as a child having WHZ  $\geq -2$  on two consecutive visits and no acute complication or edema for the past 7 days OR MUAC of  $\geq 125$ mm on 2 consecutive visits and no acute complication or edema for the past 7 days. The criteria chosen to define the recovery will be the same one we used to admit the child into the program.

- **Time to recovery.** Time from enrollment to nutritional recovery (defined above) will be calculated in days by subtracting the date of enrollment from the date of nutritional recovery.
- **Nonresponse at 8 weeks.** Nonresponse will be documented if a child does not meet the criteria for nutritional recovery at 8 weeks.
- **Transfer to inpatient care.** The occurrence, date, and reason for transfer from outpatient to inpatient treatment will be recorded.
- **Mortality by 8 weeks.** Vital status will be assessed at all follow-up time points and mortality will be defined as death during the study period. Date of death will be recorded.
- **Clinical signs of infection.** At all follow-up time points, clinical signs of infection will be recorded, including care-giver reported experience of fever, diarrhea, vomiting, and respiratory infection/cough and clinical diagnoses made at by site personnel
- **Adverse events.** Adverse events will be reported at all follow-up time points (defined in Section 5).
- **HAZ.** Height or length will be measured at all follow-up time points and height-for-age z-scores will be calculated.
- **MUAC.** Mid-upper arm circumference will be measured at all follow-up time points.
- **WAZ.** Weight will be measured at all follow-up time points and weight-for-age z-scores will be calculated.
- **WHZ.** Weight and height, assessed at all follow-up time points, will be used to calculate weight-for-height z-scores.
- **Malaria.** Rapid diagnostic tests for malaria will be conducted at baseline and week 8 to determine malaria infection status.
- **Intestinal microbiome:** Rectal swabs will be collected in a random subset of children at baseline and at week 8.

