### 9.2. Statistical Analysis

**Baseline characteristics.** Characteristics of the study population collected at baseline will be summarized using frequencies and percentages for categorical variables and means and standard deviations or medians and inter-quartile ranges for continuous variables. Baseline characteristics will be compared by treatment arm using Fisher's exact test for categorical variables and t-tests or Wilcoxon rank-sum tests for continuous variables.

**Specific Aim 1.** The primary analysis will compare weight gain velocity (g/kg/day) between groups over the 8-week follow-up period,. We will estimate mean differences and 95% confidence intervals for the difference using a linear regression model with an indicator for study group.

$$E[Y | X = x] = \beta_0 + \beta_1 X + e$$

Where:

- $Y$  = weight gain velocity from enrollment to 8 weeks
- $X$  = binary indicator for treatment group ( $X=1$  for azithromycin,  $X=0$  for a short course of oral amoxicillin)
- $\beta_1$  = difference in weight gain velocity between the azithromycin group compared to a short course of oral amoxicillin group

- $e \sim N(0, \sigma^2)$

**Specific Aim 2.** The primary analysis will compare nutritional recovery by 8 weeks from baseline by arm. We will use log-binomial regression for this analysis to estimate the risk ratio. We will use the following model:

$$\log[P(Y = 1|X_1 = x_1)] = \beta_0 + \beta_1 X_1 + e$$

Where:

- $Y$  = binary indicator for nutritional recovery by 8 weeks ( $Y=1$  for recovered,  $Y=0$  for not recovered)
- $X$  = binary indicator for treatment arm ( $X=1$  for azithromycin,  $X=0$  for a short course of oral amoxicillin)
- $e^{\beta_1}$  = relative risk of nutritional recovery in azithromycin arm compared to a short course of oral amoxicillin arm
- $e \sim N(0, \sigma^2)$

If the log-binomial model fails to converge, we will use a modified Poisson model with robust standard errors as an alternative.

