### **Secondary outcomes.**

Time to event outcomes (time to recovery and time to mortality) will be assessed visually using Kaplan-Meier curves and compared by arm using the log-rank test.

Binary outcomes will be analyzed using modified Poisson regression for rare outcomes (e.g. mortality) or log-binomial regression for common outcomes (e.g. malaria), using models similar to the one described above for Specific Aim 2.

Anthropometric assessments will be analyzed using linear models as described for Specific Aim 1, with correction for baseline values. For anthropometric assessments, z-scores will be calculated based on the 2006 WHO Child Growth Standards. Anthropometric z-scores will be analyzed as continuous variables and secondary analyses will explore categorization.

All analyses will be intention-to-treat. A significance level of 0.05 for inference and 95% confidence intervals will be reported for all effect estimates. All analyses will be conducted using R (R Foundation for Statistical Computing, Vienna, Austria). For all models, model diagnostics will be conducted to assess appropriate fit.

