### **Missing data.**

If  $\leq 10\%$  of enrolled children is missing outcome data, complete case analyses will be conducted. If  $>10\%$  of enrolled children are missing outcome data, inverse probability weighting will be used to weight complete cases by the inverse of an estimate of the probability of an outcome being observed as a sensitivity analysis. Weights will be constructed with the following baseline characteristics chosen as factors likely to predict follow-up: SES, distance from CSPS, WHZ, and MUAC.

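### The Aim 2 recovery model has only the arm term, although each child's starting point on the measure that defines recovery is known before randomization: a modest, avoidable loss of precision

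*Combined protocol and SAP*

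**What the plan says.** **The model.** Section 9.2, Specific Aim 2: "We will use log-binomial regression for this analysis to estimate the risk ratio". The equation has an intercept and one regressor, described as a "binary indicator for treatment arm". The fallback changes the estimator but adds no covariate: "If the log-binomial model fails to converge, we will use a modified Poisson model with robust standard errors as an alternative". No adjusted analysis of recovery is planned, even as a sensitivity analysis.

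**The outcome.** Section 2.5: "Nutritional recovery will be defined as a child having WHZ" of at least -2, or MUAC of at least 125 mm, held over two visits in a row without oedema or an acute complication in the preceding week. It adds: "The criteria chosen to define the recovery will be the same one we used to admit the child into the program". Each child is therefore judged on one measure only.

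**What is known at baseline.** Section 2.3: "The baseline assessment includes data collection on demographics and socioeconomic status, anthropometric assessments, and a malaria rapid diagnostic test". Randomization follows that assessment. Section 3.2 lists height or length, weight and MUAC at baseline, so both WHZ and MUAC exist for every child. Section 2.3 describes 1:1 allocation and no stratification on severity.

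**How baseline is used elsewhere.** For the continuous measures, Section 9.2 (Secondary outcomes) says: "Anthropometric assessments will be analyzed using linear models as described for Specific Aim 1, with correction for baseline values". The missing-data weights use "SES, distance from CSPS, WHZ, and MUAC", but only in a sensitivity analysis when more than 10% of outcomes are missing. Baseline characteristics are tested between arms, but no step acts on the result.

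**The concern.** A child who starts further below the recovery threshold has further to go, so the starting value on the admission measure should predict recovery. The plan accepts this reasoning for continuous WHZ and MUAC, which it corrects for baseline. It does not apply it when the same measurements are cut at a threshold, although recovery has its own aim and its own power statement.

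Two things are at stake. The interval for the risk ratio is somewhat wider than the collected data require. A chance difference in starting severity between arms of about 135 children also stays in the Aim 2 estimate. If such a difference appears in the baseline table, the plan has no prespecified response, and any adjustment made then would be post hoc.

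**Working it through.** **1. The plan's own figure.** Inputs from Section 9.1: 66% recovery on amoxicillin, a 15-point difference (so 81%), alpha 0.05 (taken as two-sided), 300 children with 10% loss, hence 270 evaluable or 135 per arm. Pooled two-proportion formula, mean proportion 0.735:

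- n per arm = [1.96 × √(2 × 0.735 × 0.265) + 0.842 × √(0.66 × 0.34 + 0.81 × 0.19)]² / 0.15² = (1.223 + 0.518)² / 0.0225 ≈ 134.7, i.e. 135
- power at 135 per arm = Φ[(0.15 × √135 − 1.223) / 0.615] = Φ(0.845) = 80.1%
- 270 / 0.9 = 300

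The stated 80% reproduces for the unadjusted comparison.

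**2. Unadjusted precision.** SE of log RR = √[0.34/(135 × 0.66) + 0.19/(135 × 0.81)] = 0.0745. At the planned RR of 0.81/0.66 = 1.227, the 95% interval is 1.06 to 1.42.

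**3. Gain from adjustment.** The documents give no prognostic strength, so the odds ratio (OR) per SD of baseline is an assumption, shown as a range. SE ratios (adjusted to unadjusted) come from simulation at 135 per arm, 66% vs 81%, each child judged on the admission criterion, with an assumed WHZ–MUAC correlation of 0.3 to 0.6. Simulated power comes from 4,000 trials per row with one covariate representing the child's severity and a standardised risk ratio.

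| OR per SD | SE ratio: own-criterion value plus admission criterion | SE ratio: WHZ and MUAC as plain main effects | Simulated power, unadjusted to adjusted |
|---|---|---|---|
| 1.5 | 0.98 | 0.99 | 80.4% to 81.2% |
| 2 | 0.95 | 0.98 to 0.99 | 80.4% to 83.7% |
| 3 | 0.91 | 0.96 to 0.97 | 79.9% to 86.8% |

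Arithmetic check on power: 80% power corresponds to a noncentrality of 1.96 + 0.84 = 2.80. Dividing by the SE ratio gives Φ(2.80/0.98 − 1.96) = 81.5%, Φ(2.80/0.95 − 1.96) = 83.8% and Φ(2.80/0.91 − 1.96) = 86.8%.

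Formula check: if baseline explains a share R² of the outcome variance, effective n per arm = 135/(1 − R²). R² of 0.05, 0.10 and 0.20 gives 142.1, 150.0 and 168.8 per arm, and power of 82.1%, 84.1% and 88.1%. At R² = 0.10 the interval in step 2 becomes 1.07 to 1.41. In the simulation, ORs of 1.5, 2 and 3 corresponded to control-arm R² of 0.035, 0.09 and 0.19.

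Choice of estimator: modified Poisson with two covariates, one of them uninformative (1,500 trials), gave 81.6% to 82.6%, 80.0% to 83.5% and 80.3% to 84.6%. At the top of the range the gain therefore depends on the estimator.

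**4. If baseline predicts nothing (OR 1).** Power went from 79.9% to 79.3% with one covariate and from 78.9% to 78.7% with two. The penalty is negligible.

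**5. Chance imbalance.** The SE of the difference in baseline means is √(2/135) = 0.12 SD. Recovery probability changes by 0.088 (OR 1.5) to 0.200 (OR 3) per SD.

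- A one-SE imbalance shifts the recovery difference by 0.088 × 0.1217 = 1.1 points up to 0.200 × 0.1217 = 2.4 points.
- A 1.96-SE imbalance (0.24 SD) shifts it by 2.1 to 4.8 points, against the 15-point target.
- On the ratio scale, the unadjusted log RR moved by 0.095, 0.17 and 0.24 per SD of imbalance. At 0.24 SD the risk ratio shifts by about 2%, 4% and 6%. The slope for the adjusted estimate was about zero (−0.007 to 0.007).

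**6. Bias.** Mean log RR was 0.205 to 0.207 with and without adjustment. Over repeated trials the unadjusted estimate is not biased.

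**The case against.** The strongest reply is that nothing here is wrong. Randomization makes the unadjusted risk ratio valid, its interval already allows for chance imbalance, and Section 9.1 powers Aim 2 by the same unadjusted comparison that Section 9.2 carries out. **This stands.** A reader might infer that the estimate is biased or the sample size too small. Steps 1 and 6 support neither.

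Second, the gain rests on a prognostic strength that the documents do not give, and eligibility (WHZ below -3 or MUAC below 115 mm) narrows the baseline range. This also stands, and it points to the first two rows of the table. It does not remove the case, because the penalty is negligible even if the covariate is uninformative.

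Third, a reader might infer that adding baseline WHZ and MUAC as two main effects brings the whole gain. The documents do not support that. A child admitted on MUAC is judged on MUAC alone, and a child admitted on WHZ on WHZ alone, so plain main effects mix relevant and irrelevant distances. They give about a 1% to 4% smaller standard error. In a separate simulation with correlation 0.3 and about 58% of children judged on MUAC, they recovered roughly a quarter of the available reduction (SE ratios 0.995, 0.987 and 0.975, against 0.982, 0.953 and 0.904).

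Fourth, Section 2.5 lists recovery as secondary and Section 2 calls the study a pilot. That limits the consequence. Even so, recovery has its own Specific Aim, its own 80% power statement with no margin, and what Section 9.2 terms the primary analysis for that aim.

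Finally, one might argue that baseline-corrected WHZ or MUAC and uncorrected recovery could disagree through imbalance alone. That is possible, but recovery also requires two visits and absence of complications, so disagreement could have other causes. It adds little to the case.

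**Conclusion.** The point holds as a worthwhile efficiency improvement, not as the correction of an error. The Aim 2 model leaves out a likely strong predictor that is measured before randomization at no extra cost. Own-criterion adjustment would cut the standard error of the log risk ratio by about 2%, 5% and 9% for assumed odds ratios of 1.5, 2 and 3 per SD, and raise power from about 80% to about 81%, 84% and 87%. At an odds ratio of 3 the modified Poisson simulation gave about 85%. Given the narrow eligibility range, 2% to 5% is the more plausible gain. Adjustment would also remove a shift of about 2% to 6% in the risk ratio in a trial with a 1.96-SE baseline imbalance.

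These sizes depend on the assumed odds ratios and, for the comparison of covariate sets, on the assumed WHZ–MUAC correlation. That the model is unadjusted, and that each child is judged on one criterion, comes directly from the text.

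**What to change.** In Section 9.2, Specific Aim 2, before any outcome is seen by arm:

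- Prespecify two covariates: admission criterion (WHZ or MUAC) and the child's baseline value on that criterion. The second can be the distance to the recovery threshold, standardised within criterion. An equivalent is baseline WHZ and baseline MUAC, each interacted with admission criterion.
- State how the covariate is assigned to a child who met both entry cut-offs, so that it matches the criterion on which that child's recovery is judged.
- Name one estimator in advance: modified Poisson with robust standard errors (already the plan's fallback), or a standardised risk ratio from a logistic model. Log-binomial regression with continuous covariates and risks near 80% is prone to non-convergence.
- Report the unadjusted risk ratio as a sensitivity analysis.

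The cost is a few sentences of text, a few degrees of freedom, and giving up log-binomial as the main fit. No new measurements, visits or children are needed, and the sample size can stay as it is.

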### **Secondary outcomes.**

Time to event outcomes (time to recovery and time to mortality) will be assessed visually using Kaplan-Meier curves and compared by arm using the log-rank test.

Binary outcomes will be analyzed using modified Poisson regression for rare outcomes (e.g. mortality) or log-binomial regression for common outcomes (e.g. malaria), using models similar to the one described above for Specific Aim 2.

Anthropometric assessments will be analyzed using linear models as described for Specific Aim 1, with correction for baseline values. For anthropometric assessments, z-scores will be calculated based on the 2006 WHO Child Growth Standards. Anthropometric z-scores will be analyzed as continuous variables and secondary analyses will explore categorization.

All analyses will be intention-to-treat. A significance level of 0.05 for inference and 95% confidence intervals will be reported for all effect estimates. All analyses will be conducted using R (R Foundation for Statistical Computing, Vienna, Austria). For all models, model diagnostics will be conducted to assess appropriate fit.

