## **2. STUDY DESIGN**

The proposed study is a pilot trial conducted in preparation for a future, larger trial. This randomized controlled trial is designed to determine the effect of administration of azithromycin compared to amoxicillin as part of the treatment of uncomplicated SAM in children aged 6-59 months on weight gain and nutritional recovery. We will randomize children presenting to nutritional programs at health centers in Burkina Faso to a single dose of oral azithromycin or a short course of oral amoxicillin upon admission into the program. Apart from the administration of antibiotics, all children will receive standard outpatient treatment for uncomplicated SAM as specified in the guidelines of the government of Burkina Faso, which includes therapeutic feeding with ready-to-use therapeutic food (RUTF). Enrolled children will be followed weekly at each routine clinic follow-up visit up until nutritional recovery. All enrolled children will return for a final study visit at 8 weeks following enrollment. Anthropometric and vital status data will be collected at each follow-up visit. Weight gain and nutritional recovery over the 8-week study period will be compared by arm.

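### Time to recovery is analysed by Kaplan-Meier and log-rank with no rule for children who die before recovering; report cumulative incidence with death as a competing event

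*Combined protocol and SAP*

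**What the plan says.** Section 9.2, Secondary outcomes, treats the two time-to-event outcomes alike: "Time to event outcomes (time to recovery and time to mortality) will be assessed visually using Kaplan-Meier curves", and the arms are "compared by arm using the log-rank test". No competing-event method is named.

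Section 2.5 defines the outcome: "Time from enrollment to nutritional recovery (defined above) will be calculated in days". It does not say what follow-up time is assigned to a child who never recovers. Death and transfer are separate outcomes in the same section. For death, "mortality will be defined as death during the study period", and its date is recorded. For transfer, "The occurrence, date, and reason for transfer from outpatient to inpatient treatment will be recorded". Section 2 adds: "All enrolled children will return for a final study visit at 8 weeks following enrollment".

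Aim 2 in Section 9.2 models a "binary indicator for nutritional recovery by 8 weeks" by log-binomial regression. It does not say whether a death counts as not recovered or as missing. The missing-data paragraph covers missing outcomes only; it mentions neither death nor censoring.

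**The concern.** Kaplan-Meier suits time to death. For time to recovery, death is a competing event: after it, recovery is impossible. Censoring a child at death lets that child be represented by the children still under follow-up, as if recovery would have come later at their rate. The curve then estimates recovery in a hypothetical population without deaths, not the share of enrolled children who recover.

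This matters here because the rationale in Section 1.1 is partly that azithromycin may lower mortality. If it does, censoring deaths removes part of that benefit from the recovery curve. Section 2 also calls the trial a pilot for a larger one, so an unstated rule could be carried forward.

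**Working it through.** **Inputs.** From Section 9.1: 66% recovery by 8 weeks on amoxicillin, a 15-point detectable difference, 300 randomised, 270 evaluable. From Section 1.1: a mortality reduction of nearly 14% with mass azithromycin. Death and transfer rates are not given, so failure rates of 1% to 15% are assumed and shown as a range.

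**1. The plan's own figure.** No figure is stated for time to recovery. The nearest is the Aim 2 power for 66% against 81% with 135 per arm (pooled proportion 0.735):

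z = [0.15 × √135 − 1.96 × √(2 × 0.735 × 0.265)] / √(0.66 × 0.34 + 0.81 × 0.19) = (1.743 − 1.223) / 0.615 = 0.845, so power is 80.1%. The stated 80% is reproduced, and 270 / 0.9 = 300.

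**2. Overstatement if failures are censored.** Let F be the true proportion recovered by day 56 and d the proportion that failed first. With constant hazards:

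- total cumulative hazard H = −ln(1 − F − d)
- recovery part H_R = H × F / (F + d)
- 1 − KM = 1 − exp(−H_R)

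For F = 0.66 and d = 0.01: H = −ln(0.33) = 1.109, H_R = 1.109 × 0.66 / 0.67 = 1.092, and 1 − KM = 66.45%.

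| Failures before recovery (assumed) | True recovery | 1 − KM | Overstatement (points) |
|---|---|---|---|
| 1% | 66% | 66.45% | 0.45 |
| 2% | 66% | 66.9% | 0.9 |
| 3% | 66% | 67.4% | 1.4 |
| 5% | 66% | 68.4% | 2.4 |
| 10% | 66% | 71.0% | 5.0 |
| 15% | 66% | 74.2% | 8.2 |

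A weekly simulation (recovery possible at weeks 2 to 8, failure at weeks 1 to 8, 66% recovery without failures) agrees: 0.4 to 0.5 points at 1%, 1.4 to 1.5 at 3%, about 5 at 10% and about 8 at 15%.

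**3. Masking.** Give both arms the same recovery hazard, H_R = −ln(0.32) × 0.66 / 0.68 = 1.106, so that 1 − KM = 66.9% in each. Only the failure rate differs:

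| Failures | 1 − KM | True recovery |
|---|---|---|
| 2% | 66.9% | 66.0% |
| 5% | 66.9% | 64.6% |
| 10% | 66.9% | 62.3% |
| 15% | 66.9% | 59.9% |

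The curves coincide while true recovery differs by 1.4 points (2% against 5%) to 6.1 points (2% against 15%). The arm with more failures looks equal, not better.

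**4. Reversal.** Suppose instead that every failure is a child who would not have recovered and who leaves before any recovery occurs. Then 1 − KM = F / (1 − d). With true recovery of 66% against 62% and failures of 2% against 15%, this gives 0.66 / 0.98 = 67.3% against 0.62 / 0.85 = 72.9%, so the order reverses.

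A log-rank simulation (150 per arm, 2,000 runs, 66% recovery in both arms, failures among non-recoverers in weeks 1 to 3) shows how often the test significantly favours the arm with more failures; the nominal rate is 2.5%:

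| Failures by arm | Failures censored | Failures kept unrecovered to week 8 |
|---|---|---|
| 2% vs 5% | 4.5% | 2.7% |
| 2% vs 10% | 17.5% | 2.5% |
| 2% vs 15% | 36% | 2.6% |

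**5. Scale.** In step 3, each extra point of failures hides about (66.0 − 62.3) / (10 − 2) = 0.46 points of recovery. A 14% relative difference in failures then hides about 0.14 × 0.46 = 0.06 points at 1% failures, 0.7 × 0.46 = 0.3 at 5%, and 1.4 × 0.46 = 0.65 at 10%. The standard error of the recovery difference with 150 per arm is √(2 × 0.66 × 0.34 / 150) = 5.5 points.

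**The case against.** The strongest reply is that this is a missing rule in one secondary outcome of a pilot, and small in size. Much of that stands.

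- A reader might infer that the plan censors deaths and transfers. It states no censoring rule. Kaplan-Meier with failures held unrecovered to day 56 would be sound, so the fault is the silence together with the usual default.
- A reader might treat transfer as a competing event. The documents do not support this: a transferred child can still recover, every child is due at the 8-week visit, and the analyses are by intention to treat. Section 9.2 names mortality as its example of a rare outcome, so the low rows of the table in step 2 are the relevant ones for death.
- Log-rank remains a valid test of the cause-specific recovery hazard. Gray's test addresses a different hypothesis and is not required.
- A reader might infer a conflict with Aim 2. Aim 2 does not say how a death is coded, so no conflict can be shown.
- A reader might see a broken promise in "95% confidence intervals will be reported for all effect estimates", since log-rank gives no estimate. The sentence concerns estimates that are reported, and Aim 2 supplies a risk ratio for recovery. An interval for the time-to-recovery comparison would be an improvement, not the repair of a contradiction.

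What the reply does not remove is that death makes recovery impossible, and that the named method, run in its ordinary way, does not estimate the proportion recovering.

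**Conclusion.** The point holds in limited form and is worth correcting. Under censoring at death, the recovery curve is too high by about 0.5 points at 1% deaths and about 1.4 to 1.5 at 3%; 5 points or more requires failures near 10%. These figures rest on 66% recovery and on assumed failure rates.

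If deaths differ by arm, part of a true difference in recovery can be hidden. At a relative difference of the size cited in Section 1.1, that part is well inside sampling error. It would be wrong to conclude that the arm with more failures will look better: that needs large imbalances, such as 2% against 10% or more, concentrated in children unlikely to recover, and nothing in the documents establishes either. The primary outcome and the Aim 2 risk ratio do not use Kaplan-Meier, and the sample size is unaffected.

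**What to change.** In Section 9.2:

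- Keep Kaplan-Meier and log-rank for mortality.
- For time to recovery, report the Aalen-Johansen cumulative incidence by arm with death as a competing event. Keeping children who die in the risk set, unrecovered, to day 56 gives the same result when no child is otherwise lost before then.
- Report the day-56 difference in cumulative incidence with a 95% confidence interval. The log-rank test may stay if it is labelled as a test of the cause-specific recovery hazard.
- Do not censor at inpatient transfer. Keep transferred children in follow-up, count recovery if the criterion is later met, and otherwise count them as not recovered at day 56.
- Code deaths as not recovered in Aim 2, so that both recovery analyses use one rule.

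The cost is a paragraph of SAP text and a few lines of R; dates of death and transfer are already to be recorded. The curve will sit slightly lower than a Kaplan-Meier curve. Recovery dates after transfer may be known only to the next study visit. Because recovery requires two consecutive qualifying visits, the SAP should also say how a transferred child seen only at week 8 is classified.

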## 9. STATISTICAL METHODS

### 9.1. Sample Size and Power

**Specific Aim 1** We assume that inclusion of 300 children (150 randomized to each arm) will provide 80% power to detect a 27% increase in weight gain (g/kg/day) in children receiving azithromycin compared to children receiving amoxicillin at an alpha of 0.05. Assumptions for this calculation were based on the pattern of weight gain reported in a trial of routine amoxicillin for uncomplicated SAM in Niger comparing children receiving amoxicillin to placebo over time. We assumed an average weight gain of 4.9 g/kg/day in the amoxicillin arm, with a standard deviation of 3.9 g/kg/day, and loss to follow-up of 10%. A 27% increase corresponds to a mean difference in weight gain of 1.3 g/kg/day, or an average weight gain of 6.2 g/kg/day in the azithromycin arm.

This calculation was performed in Stata using the following command:

```
power twomeans 4.9, sd(3.9) alpha(0.05) power(0.8) n(270)
```

**Specific Aim 2.** Inclusion of 300 children (150 randomized to each arm) will provide 80% power to detect an 15 percentage point difference in the proportion of children achieving nutritional recovery in the azithromycin arm compared to the amoxicillin arm. Assumptions for this calculation were based on nutritional recovery reported in the amoxicillin arm of a trial of routine amoxicillin for uncomplicated SAM in Niger. We assumed that 66% of children in the oral amoxicillin arm would achieve nutritional recovery and a loss to follow-up of 10%.

This calculation was performed in Stata using the following command:

```
power twoproportions 0.66, alpha(0.05) power(0.8) n(270)
```

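### Modified Poisson regression, planned for rare outcomes such as mortality, breaks down when one arm has no events, and the plan has no rule for that case

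*Combined protocol and SAP*

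**What the plan says.** Section 9.2, Secondary outcomes, assigns the method: "Binary outcomes will be analyzed using modified Poisson regression for rare outcomes (e.g. mortality"). It adds that the models resemble the one for Specific Aim 2, which has a log link and a single treatment indicator whose exponentiated coefficient is the risk ratio.

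The variance estimator comes from the Specific Aim 2 text, where the method is introduced as the fallback if the log-binomial model does not converge: "we will use a modified Poisson model with robust standard errors as an alternative". That fallback leads to modified Poisson; nothing leads away from it.

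Four other statements bear on the point:

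- Reporting: "A significance level of 0.05 for inference and 95% confidence intervals will be reported for all effect estimates".
- A second mortality analysis: "Time to event outcomes (time to recovery and time to mortality) will be assessed visually using Kaplan-Meier curves", with a log-rank comparison by arm.
- A general check: "For all models, model diagnostics will be conducted to assess appropriate fit".
- Fisher's test appears only for the baseline table: "Baseline characteristics will be compared by treatment arm using Fisher's exact test for categorical variables".

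No section says what to report when an arm has no events. There is no exact method, penalised fit, continuity correction or minimum event count.

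**The concern.** An arm with no deaths is a foreseeable result for an outcome the plan itself calls rare, with 150 children per arm. The log risk ratio then diverges. A model-based standard error would diverge with it and give p near 1. The robust standard error does not diverge, so the fit looks precise and overwhelmingly significant, even when one child has died in the whole trial.

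At stake are the risk ratio and 95% CI that the plan promises for every effect estimate, and the p-value attached to them. In the smallest tables the two planned mortality analyses would also contradict each other, and the plan does not say which governs. Transfer to inpatient care (Section 2.5: "The occurrence, date, and reason for transfer from outpatient to inpatient treatment will be recorded") is not among the listed time-to-event outcomes. If the team treats it as rare, it has no log-rank result to fall back on.

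**Working it through.** **Inputs.** Section 9.1: 300 children, 150 per arm, 10% loss, so 300 × 0.9 = 270 or 135 per arm, matching "power twoproportions 0.66, alpha(0.05) power(0.8) n(270"). Section 9.2: α = 0.05, analysis in R. The plan states no figure for mortality to reproduce, so death rates below are assumptions, shown as a range.

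**Robust variance.** In a Poisson model with one binary covariate, an arm with k events among n children contributes (1 − k/n)/k to the sandwich (HC0) variance of the log risk ratio. In an empty arm with fitted mean μ, the contribution is nμ²/(nμ)² = 1/n, however small μ becomes. For 0 v k with equal arms:

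variance = 1/n + (1 − k/n)/k = 1/k, so SE = √(1/k).

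For k = 1, n = 150: 1/150 + 149/150 = 1, so SE = 1.00. The coefficient stops wherever the software's tolerance stops it.

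**Fit with R's default settings, azithromycin 0 v amoxicillin 1.**

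- 150 per arm: converged in 21 iterations, coefficient −18.29, robust SE 1.00. Risk ratio e^(−18.29) = 1.1e-8; 95% CI exp(−18.29 ± 1.96) = 1.6e-9 to 8.1e-8; p about 1e-74. The model-based SE of the same fit is in the thousands (p above 0.99), so the robust SE produces the rejection.
- 135 per arm: coefficient −17.40, risk ratio 2.8e-8, p about 9e-68.
- Arms reversed, 150 per arm: risk ratio 8.8e7, 95% CI 1.2e7 to 6.2e8, p about 3e-75.

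HC0, HC1 and HC3 differ by about 1%. The exact risk ratio depends on the stopping rule; the near-zero p-value appeared in every such table fitted.

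**Comparison with other tests, 150 per arm** (log-rank assumes no censoring and deaths one at a time):

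| Deaths | Modified Poisson p | Fisher p | Log-rank p |
|---|---|---|---|
| 0 v 1 | near 0 | 1.00 | 0.32 |
| 0 v 2 | near 0 | 0.50 | 0.16 |
| 0 v 3 | near 0 | 0.25 | 0.08 |
| 0 v 4 | near 0 | 0.12 | 0.044 |
| 0 v 5 | near 0 | 0.06 | 0.024 |
| 0 v 6 | near 0 | 0.03 | 0.014 |

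Neither test supports the rejection at 0 v 1 to 0 v 3. At 0 v 4 and 0 v 5 only log-rank does; from 0 v 6 both do. The risk ratio and CI are unusable in every row.

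**How often.** With equal mortality p, the chance that exactly one arm is empty is 2q(1 − q), where q = (1 − p)^n. At p = 1%, n = 150: q = 0.2215, so 2 × 0.2215 × 0.7785 = 0.345. Type I error was found by enumerating both binomial counts. Tables with one empty arm count as rejections, 0 v 0 as none, and all others by the Wald test with variance (1 − p₁)/k₁ + (1 − p₀)/k₀.

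| Assumed mortality | Type I error, 150 / 135 per arm | Share from 0 v 1 to 0 v 3, 150 / 135 |
|---|---|---|
| 0.5% | 0.50 / 0.50 | 0.49 / 0.49 |
| 1% | 0.34 / 0.38 | 0.32 / 0.36 |
| 1.5% | 0.19 / 0.23 | 0.15 / 0.19 |
| 2% | 0.096 / 0.125 | 0.058 / 0.085 |
| 2.5% | 0.052 / 0.069 | 0.021 / 0.035 |
| 3% | 0.034 / 0.043 | 0.007 / 0.013 |
| 4% | 0.028 / 0.028 | 0.001 / 0.002 |
| 5% | 0.031 / 0.030 | below 0.001 |

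The total falls below 0.05 at about 2.5% (150 per arm) or 2.8% (135). The share from 0 v 1 to 0 v 3 does so at about 2.1% or 2.3%. At 3% one arm is still empty in 2.1% or 3.2% of trials; at 5%, in 0.1% or 0.2%.

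**The case against.** **Frequency is assumed.** The documents give no death rate, and Section 1.1 presents these children as a high-mortality group. Above about 3% per arm the problem almost disappears. This stands, and it is why a range is shown. The plan's own label for mortality is nevertheless rare, which points to the part of the range where the problem matters.

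**Someone would notice.** A risk ratio of 1e-8 is conspicuous, and model diagnostics are promised, so the type I error figures are a worst case in which the output is reported unexamined. This also stands. But the diagnostics sentence names no trigger and no replacement, so the method would be chosen after deaths by arm were known.

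**Log-rank already covers mortality.** It gives a usable p-value, but not the promised risk ratio and interval, and it does not cover transfer. No passage classes transfer as rare, so that part is conditional.

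**Robust errors are not restated for secondary outcomes.** True, but that is how the plan introduces the method. With model-based errors, p would be near 1 and the interval equally useless.

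**Fisher is not the yardstick.** It is conservative, and at 0 v 4 and 0 v 5 the planned log-rank test does reject. So only 0 v 1 to 0 v 3 should be called unsupported by either test.

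**Conclusion.** The concern holds. As written, the plan yields a near-zero p-value and a meaningless risk ratio and CI whenever exactly one arm has no events, and it offers no alternative. That part is algebra and needs no assumption about mortality.

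How often it would happen rests on assumed equal death rates: serious at about 2% per arm or below, minor at 3% or above. Priority is low to moderate. The trial is a pilot, both specific aims are untouched, and log-rank remains for mortality. It is worth correcting because the fix is short and mortality is the plan's own example for this method.

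**What to change.** Add to Section 9.2, Secondary outcomes:

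> When either arm has zero events, no modified Poisson estimate, CI or p-value will be reported; event counts by arm, Fisher's exact test and a risk difference with a Newcombe 95% CI will be reported instead, and the test decision for the binary outcome rests on Fisher's p-value. For mortality, the log-rank test is reported as the separate time-to-event analysis.

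Keep the regression when both arms have events. The rule also covers 0 v 0.

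Under this rule, type I error at assumed rates of 0.5/1/1.5/2/2.5/3% is 0.000/0.002/0.006/0.012/0.016/0.020 at 150 per arm and 0.000/0.001/0.005/0.010/0.014/0.018 at 135. Newcombe intervals at 150 per arm, in percentage points: 0 v 0, −2.5 to 2.5; 0 v 1, −3.7 to 1.9; 0 v 3, −5.7 to 0.8; 0 v 4, −6.7 to 0.3.

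The cost is two sentences and one added interval method. Fisher's test is conservative, and no risk ratio is given in these tables, so the effect measure depends on the data. The rule also introduces a disagreement between Fisher and log-rank at 0 v 4 and 0 v 5. At 0 v 5 the Newcombe interval (−7.6 to −0.2 points at 150 per arm, −8.4 to −0.2 at 135) excludes zero while Fisher gives p = 0.06. The text therefore names the deciding test in advance.
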